6.3 Concomitant Medications and Procedures

A concomitant medication is defined as any prescription or OTC preparation, including vitamins, medications, vaccinations, herbal preparations, and supplements (including traditional Chinese medicine) that is taken by a subject during the conduct of the clinical trial.

All concomitant medications taken during the study from the date the ICF is signed through the end of study participation ([Section 4.4](#)) (ie, completion of the follow-up period or the subject is “lost to follow-up”) must be recorded in the subject’s source documentation. This information should include the name of the medication, the start and stop dates, the dosage, route of administration, and the indication for which the concomitant medication was administered. Medications taken for a procedure will also be included. Concomitant medications will be coded using the World Health Organization Drug Reference List.

Elective procedures should not be performed during the study.

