6.3.1 Prohibited Concomitant Therapy

As the potential for drug-drug interactions between ABI-4334 and other compounds has not yet been fully evaluated, all concomitant medications (defined in [Section 6.3](#)) being taken at the time of Screening, except for paracetamol (also known as acetaminophen), should be washed out beginning 14 days or 5 half-lives whichever is longer prior to Day 1 dosing. Paracetamol (up to 4 g/day) and topical agents are allowed, as needed (PRN) during the course of the study at the Investigator's discretion. All other concomitant medications are prohibited through end of study.

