5.4.1 Prior Medications

Prior medications will be defined as any medications taken before a subject took the first study drug. Prior medications will be summarized by Anatomical Therapeutic Chemical (ATC) drug class Level 2 and preferred name using the number and percentage of subjects for each treatment and cohort. A subject reporting the same medication more than once will be counted only once within each ATC drug class. The summary will be ordered alphabetically by ATC medical class

and then by preferred term in order of descending overall frequency within each ATC medical class. For drugs with the same frequency, sorting will be done alphabetically.

A medication will be considered as a prior medication if it meets one of the following criteria:

- A medication with a start date prior to the first dose date of study drug will be included in the prior medication summary regardless of when the stop date is.
- If a partial start date is entered, the medication will be considered prior unless the month and year (if day is missing) or year (if day and month are missing) of the start date are after the first dose date.
- A medication with a completely missing start date will be included in the prior medication summary, unless otherwise specified.

Summaries will be based on the Safety Analysis Set.

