5.4.2 Concomitant Medications

Concomitant medications will be defined as any prescription or over-the-counter preparation, including vitamins, medications, vaccinations, herbal preparations, and supplements (including traditional Chinese medicine) taken by a subject during the study. Use of concomitant medications will be summarized by ATC drug class Level 2 and preferred name using the number and percentage of subjects for each treatment and cohort. A subject reporting the same medication more than once within each ATC drug class will be counted only once when calculating the number and percentage of subjects who received that medication. Medications may appear under multiple ATC drug classes. The summary will be ordered alphabetically by ATC medical class and then by preferred term in descending overall frequency within each ATC medical class. For drugs with the same frequency, sorting will be done alphabetically.

A medication will be considered as a concomitant medication if it meets one of the following criteria:

- A medication with a start date prior to or on the first dose date of study drug, and continued to be taken after the first dose date.
- A medication started after the first dose date but prior to or on the last dose date of study drug.
- If a partial start date is entered, any medication with the month and year (if day is missing) or year (if day and month are missing) before the study drug stop date, and with the stop date after the first dose date of study drug. If a partial stop date is entered, any medication with the month and year (if day is missing) or year (if day and month are missing) after the first dose date of study drug.

- A medication started and stopped on the same day as the first dose date or the last dose date of study drug.
- Medications with completely missing start and stop dates, unless otherwise specified.

A medication with a stop date prior to the date of first dose date of study drug or a start date after the last dose date of study drug will be excluded from the summary.

Summaries of prior and concomitant medications will be based on the Safety Analysis Set.

All the prior and concomitant medications will be provided in a by-subject listing sorted by cohort, subject number, and administration date in chronological order.

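### SAP 5.4.2 defines concomitant medication as taken during the study, yet a medication with a complete start date after the last dose enters neither summary table

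*Combined protocol and SAP*

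**What the plan says.** The definition sentence in SAP 5.4.2 covers any preparation "taken by a subject during the study". The criteria below it are narrower. For starts after first dose, the second bullet admits "A medication started after the first dose date but prior to or on the last dose date of study drug". The closing rule repeats that limit: a medication with "a start date after the last dose date of study drug will be excluded from the summary".

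SAP 5.4.1 governs the other table: "A medication with a start date prior to the first dose date of study drug will be included in the prior medication summary". No third medication table is planned. Section 5.4.2 ends with a by-subject listing of all prior and concomitant medications.

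The protocol uses a longer window. Section 6.3 requires recording of "All concomitant medications taken during the study from the date the ICF is signed through the end of study participation". Section 6.3.1 allows paracetamol and topical agents as needed and then states: "All other concomitant medications are prohibited through end of study".

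**The concern.** The definition and the criteria in the same SAP section disagree on the time window. The criteria decide what is programmed, so the table will hold less than its definition promises. The gap is widest in the single-dose cohorts, where almost the whole observation period falls after the last dose.

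The cut-off also departs from the other safety summaries. Treatment-emergent adverse events run to end of study (SAP 5.1.5.1). Laboratory and vital-sign changes from baseline include follow-up visits (SAP 5.2.3 and 5.3). If paracetamol were started on Day 3 in Cohort A2 for a headache, the headache would be counted and the paracetamol would not.

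**Working it through.** The plan gives no figure to reproduce. The check is a trace of the rules followed by a count of days.

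**Inputs**
- A1-A5: first dose = last dose = Day 1 (Protocol Appendix 1a marks Day 1 as last day of dosing; SAP 4.3.1 expects 1 day of exposure in Part A).
- A1-A5 end of study: Day 7 in Appendix 1a. Protocol 4.4 gives 1 day of treatment plus 7 of follow-up, hence Day 8. Both are carried.
- Part B: last dose Day 8; end of study 7 days later (Appendix 2), so 8 + 7 = Day 15.

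**Trace: A1-A5, complete start date on Day 3**
- Prior (5.4.1): needs start < Day 1. Fails.
- 5.4.2 bullet 1: needs start ≤ Day 1 and continued use. Fails.
- Bullet 2: needs Day 1 < start ≤ Day 1. No date can satisfy this.
- Bullet 3: the first sentence needs a partial start date, the second a partial stop date. Neither applies to a fully dated record.
- Bullet 4: needs start and stop on the first or last dose date. Fails.
- Bullet 5: needs missing start and stop dates. Fails.
- Exclusion sentence: Day 3 > Day 1, so the record is removed.

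Result: neither table.

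**Days on which a fully dated new start is untabulated (first dose to end of study)**
- A1-A5, Appendix 1a: Days 2-7, 6/7 = 86%.
- A1-A5, Protocol 4.4: Days 2-8, 7/8 = 88%.
- Part B: Days 9-15, 7/15 = 47%.

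Applying the complete-date rules to every start day from Day -28 to end of study, with every possible stop day or ongoing use, gives the same sets of days.

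**A6 and A7.** The SAP does not say whether the last dose date is taken per subject, per cohort or per period. Taken within A6, the count matches A1-A5. For A7, if the last dose is the Period 2 dose and that falls on Day 8 (assumed: the minimum 7-day washout), end of study is Day 14 and Days 9-14 are lost, 6/14 = 43%. Starts between the two doses would then be counted.

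**Incomplete dates.** A start date with the day missing, in the month of first dose, goes to the prior table under 5.4.1. The partial-start rule in 5.4.2 also ends at dosing: the start must be "before the study drug stop date, and with the stop date after the first dose date of study drug". The next clause ("If a partial stop date is entered, any medication with the month and year") puts no upper limit on the start date, so a record with a complete start after last dose and a partial stop in a later month meets that criterion. Only the exclusion sentence then removes it.

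**The case against.** The best defence is that the cut-off is deliberate. The second bullet and the exclusion sentence state the same limit, and the rule for complete dates can be programmed as it stands. The protocol's planned analyses (Section 10.4) promise no concomitant-medication table; Protocol 6.3 asks only for recording and coding. The empty second bullet in A1-A5 does no harm to Day 1 starts, which bullet 1 or bullet 4 picks up. With about 8 subjects per cohort, the listing can be read subject by subject.

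Much of this stands. No protocol commitment is broken, and an on-treatment table would be a legitimate choice. But the SAP neither labels the table on-treatment nor limits the definition to treatment, and a listing does not make a table complete against its own definition.

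A reader might go further and infer that follow-up medications vanish from the study report. The documents do not support that: the exclusion is only from the summary, so the listing should still show them. Nor would prohibited use in follow-up go unseen, since SAP 4.2 lists all protocol deviations. The day percentages should not be read as shares of medications or of subjects; the documents give no basis for estimating how many records are affected.

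**Conclusion.** Wrong as written, with limited weight. SAP 5.4.2 contradicts its own definition, and a medication with a complete start date after the last dose is in neither table. The untabulated window is 6 of 7 days in A1-A5 (7 of 8 on Protocol 4.4's durations) and 7 of 15 in Part B.

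This rests on complete start dates and on the last dose date being taken within each cohort. Few records are expected, because Protocol 6.3.1 permits so little. No endpoint, analysis population or inference changes. The consequence is an incomplete safety table that does not line up with the adverse event tables beside it.

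**What to change.** In SAP 5.4.2:
1. Change the second bullet to cover medications started after the first dose date and on or before end of study.
2. Exclude from the summary only medications stopped before the first dose date or started after end of study.
3. In the partial-start-date rule, replace the study drug stop date limit with: the same as or before the month and year (or year) of end of study.
4. For subjects returning in A6, assign a new start on or after the A6 dose date to A6 only, so that it is not counted in both cohorts. A7 needs no per-period cut-off, because SAP Section 3 presents its tables by fasting order.

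With items 1 and 2, every complete start date after first dose and up to end of study meets the second bullet, so no such day is left untabulated in any cohort.

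If an on-treatment table is what the sponsor wants, label it so and narrow the definition sentence, noting that in A1-A5 it would cover new starts on Day 1 only.

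The cost is a small SAP edit, one assignment rule for A6 in programming, and slightly larger table counts. Medications are already recorded to end of study, so no new data are needed.

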5.5 Electrocardiogram Results

A shift table of the Investigators' assessment of electrocardiogram (ECG) results at each visit compared with Baseline values will be presented by treatment and cohort using the following categories:

- normal
- abnormal (not clinically significant)
- abnormal (clinically significant)
- missing/not done

The number and percentage of subjects in each cross-classification group of the shift table will be presented. Subjects with a missing value at Baseline or post-Baseline will not be included in the denominator for percentage calculation.

A by-subject listing for ECG assessment results will be provided by cohort, subject number, and visit in chronological order.

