10.4 Planned Analyses

All safety and PK endpoints will be summarized using descriptive statistics by treatment. Continuous endpoints will be described using the mean, standard deviation, median, minimum, and maximum. Categorical endpoints will be described using the number and percent of subjects who meet the endpoint criterion. The safety and PK analyses will be presented according to the treatment received. Due to sample size limitations, no formal statistical inference is planned.

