10.4.4 Analysis of Safety Endpoints

The safety parameters to be assessed are described in [Section 8.3](#). Displays for safety results will utilize descriptive statistics. No formal hypothesis testing of safety data is planned.

Adverse events will be coded using the Medical Dictionary for Regulatory Activities (MedDRA). A treatment-emergent adverse event (TEAE) will be defined as any AE that has an onset date or worsening in severity from Baseline on or after the first dose of study drug through end of study (defined in [Section 4.5](#)). Incidence of each body system and preferred term will be tabulated for each treatment. Summaries will include all TEAEs, TEAEs considered related to study treatment by the Investigator, graded TEAEs, serious TEAEs, TEAEs leading to premature discontinuation from the study intervention. All AEs, emergent or nonemergent, will be listed by subject.

Clinical laboratory results will be summarized descriptively by treatment including values, changes from Baseline, and incidence of laboratory abnormalities. Laboratory results will be listed for each subject.

Vital signs data and ECG findings reported at each visit will be displayed by treatment, using descriptive statistics for observed and change from Baseline values.

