Confined to Study Clinic	X	X	X	X				
Discharge					X			
Complete Physical Exam	X				X ^c			
Symptom-Directed Physical Exam		X	X	X		X	X	X
Vital Signs ^a	X	X	X	X	X	X	X	X
12-Lead ECG ^a		X	X		X			X
Weight	X							X
Concomitant Medications & Adverse Events	X	X	X	X	X	X	X	X
Alcohol Testing	X							
Urine Drug Test	X							
Urine pregnancy test (females of childbearing potential) ^b		X			X			
Confirm Subject Eligibility	X	X						
In Clinic Study Drug Dosing		X						
Laboratory Assessments								
Chemistry		X ^c	X	X		X		X
Hematology		X ^c	X	X		X		X
Coagulation		X ^c	X	X				X
Urinalysis		X ^c	X	X				X
Serum Pregnancy Test (females of childbearing potential) ^b	X							
Pharmacokinetics Assessments								
PK Sampling ^d		X	X	X	X	X	X	X

Abbreviations: ECG=electrocardiogram; EOS=end of study LDD=last day of dosing; NA=not applicable; PK=pharmacokinetic

Note: When multiple procedures are scheduled at the same time, the order of events will be: 12-lead ECGs, vital signs, PK blood sample collection (to be collected on the scheduled time point), and meals.

ABI-4334

Study ABI-4334-101 Original Protocol 16 June 2022

- ^a Collection of vital signs and ECG will be repeated throughout the day. Specifically, vital signs will be collected predose (within 2 hours before dosing) on Day 1, and at 2, 4, 8, 12, 24, 48, 72, 96, 120, and 144 hours after dosing on Day 1. Collection of ECG will be performed predose on Day 1, and at 2, 4, 12, and 24 hours (ie, Day 2) after dosing on Day 1; and anytime on Days 4 and 7. The window for collection of vital signs and ECGs will be ± 15 minutes.
- ^b A serum pregnancy test is required at Day -1 for female subjects of childbearing potential. On Day 1, a urine pregnancy test will be performed for females of childbearing potential, prior to dosing. All post Day 1 pregnancy tests may be conducted by urine dipstick. If positive on dipstick, reflex to serum.
- ^c On Day 1, samples for clinical laboratory tests will be taken predose.
- ^d Blood samples for PK analysis of ABI-4334 in plasma will be collected at the following time points: predose (within 0.5 hours before dosing) and 0.5, 1, 2, 3, 4, 5, 6, 9, 12, 18, 24, 36, 48, 72, 96, 120, and 144 hours after dosing on Day 1; Time point windows are ± 2 minutes for 0.5- and 1-hour postdose samples and ± 5 minutes for samples from 2 through 18 hours postdose and ± 30 minutes for samples 24 hours postdose and after.

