The DRC will select a single dose level from Cohorts A1-A5 for evaluation of food effect. The selection of this dose level can be made prior to completion of all fasted SAD cohorts and will be based on a preliminary evaluation by the DRC of the available safety, tolerability, and PK data from selected Cohorts A1-A5. Subjects who complete participation in this selected cohort will be asked to return to the study site to be enrolled into the food-effect cohort (ie, Cohort A6), following a minimum of 7-day washout period since their last study drug dose. While Baseline evaluations will be conducted prior to dosing in Cohort A6, repeat assessment of all study eligibility criteria will not be performed. Returning subjects will retain their original subject number and randomized treatment assignment. After the Day 7 visit in the original cohort (from Cohort A1-A5), the study drug will be administered 30 minutes after the complete consumption of a high fat meal (approximately 50% calories from fat).

If there is an insufficient number of subjects from previous fasted SAD cohorts (ie, A1-A5), who are willing to participate in Cohort A6, then a separate Cohort A7 may be enrolled, comprising 6 new subjects meeting the study eligibility criteria, who will all receive ABI-4334. Cohort A7 will

involve a two-period crossover assessment of food effect (ie, Period 1: dosing under fasted or high fat-fed conditions; Period 2: dosing under condition opposite of Period 1), with a minimum 7-day washout period between dosing in Period 1 and Period 2, and a 7-day postdose follow-up in Period 2.

[figure not shown]

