3.5.4 Definition of Baseline

For all analyses, Baseline will be defined as the last non-missing evaluation prior to the first dose date/time. For cohort A7, Period 2 Baseline will be defined as last non-missing evaluation prior to the dosing on Period 2 Study Day 1.

For all cohorts, except cohort A7 Period 2, Change from Baseline will be defined as the result at desired timepoint minus the result at Baseline. For cohort A7 Period 2, Change from Baseline will be defined as the result at desired timepoint minus the result at Period 2 Baseline.

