5.3 Body Weight and Vital Signs

Descriptive statistics will be provided by treatment and cohort for body weight, BMI, and vital signs (systolic and diastolic blood pressure [mmHg], pulse [beats/min], respiration [breaths/min], and body temperature [°C]) as follows:

- Baseline value
- Values at each post-Baseline visit
- Change from baseline at each post-Baseline visit

A Baseline value will be defined as the last available value collected on or prior to the date/time of first dose of study drug. Change from Baseline to a post-Baseline visit will be calculated for any post-Baseline visit including follow-up visits.

For Cohort A7 Period 2, Period 2 Baseline and Change from Period 2 Baseline will be used instead.

In the case of multiple values in an analysis window, data will be selected for analysis as described in [Section 3.5.6](#).

A by-subject listing of vital signs will be provided by cohort, subject number, and visit in chronological order. In the same manner, a by-subject listing of body weight, height, and BMI will be provided separately.

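### Protocol 10.4.4 promises observed and change-from-Baseline statistics for ECG, but SAP 5.5 plans only a shift table of the Investigator's overall reading and a listing, with no reason given

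*Combined protocol and SAP*

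**What the plan says.** Protocol 10.4.4 (Analysis of Safety Endpoints) deals with vital signs and ECG together. On the ECG side it says that "ECG findings reported at each visit will be displayed by treatment, using descriptive statistics for observed and change from Baseline values". Protocol 10.1 adds that the SAP will be complete and will describe every planned analysis.

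The SAP splits the two data types. Section 5.3 summarises vital signs as Baseline value, value at each later visit, and change from Baseline. Section 5.5 plans a shift table of the Investigators' assessment, in which "electrocardiogram (ECG) results at each visit compared with Baseline values will be presented by treatment and cohort using the following categories". There are four of these: normal, abnormal not clinically significant, abnormal clinically significant, and missing or not done. The only other ECG output is a by-subject listing.

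SAP 3.5.4 fixes the meaning of the key term: "Change from Baseline will be defined as the result at desired timepoint minus the result at Baseline".

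**The concern.** The protocol makes the same commitment for vital signs and for ECG. The SAP keeps it for the first and replaces it for the second without comment. An overall reading of normal or abnormal is not a measured value, and its movement between categories is not a difference.

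At stake is the description of cardiac safety in a first-in-human trial whose primary objective is safety and tolerability. A PR or QTc change that leaves the overall reading in the same category, and is not recorded as an AE, would appear in no summary table. A change that moves the reading to another category would be counted, but its size would not be shown.

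**Working it through.** The plan gives no figure to reproduce here. The check is a comparison of texts, followed by arithmetic on the protocol's own grading limits.

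**1. Promise against delivery**

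| Item | Protocol 10.4.4 | SAP |
|---|---|---|
| Vital signs, observed | yes | yes (5.3) |
| Vital signs, change from Baseline | yes | yes (5.3) |
| ECG, observed | yes | categories only (5.5) |
| ECG, change from Baseline | yes | category shift only (5.5); no difference as defined in 3.5.4 |

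**2. Whether another section fills the gap**

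- SAP 3 states the general descriptive statistics but names no ECG variable.
- SAP 5.2.1 applies the Appendix 4 grades to laboratory results only, so no planned table uses the PR and QTc limits.
- Protocol 8.3.4 has Holter data stored for possible later analysis, with no analysis planned.
- SAP 1 provides for documenting changes made after the SAP is final. It does not cover departures from the protocol.

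**3. What the shift table can show**

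There are 3 non-missing categories at Baseline and 3 at the visit, so 3 × 3 = 9 cells. In the 3 same-category cells an interval change of any size is invisible. In the other 9 − 3 = 6 cells a shift is counted without its size.

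**4. Can a change that matters by the protocol's own limits go unseen?**

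Inputs, from protocol Appendix 4: QTc Grade 1 starts at 0.45 s (450 ms); a rise of 0.06 s (60 ms) or more over baseline is one of the Grade 3 criteria; PR Grade 1 starts at 0.21 s (210 ms).

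- QTc: 450 − 60 = 390 ms. A 60 ms rise from any Baseline below 390 ms meets the Grade 3 change criterion while ending below 450 ms. Assumed example: 445 − 385 = 60 ms, and 445 < 450.
- PR: a rise ending below 210 ms reaches no grade. Assumed example: 195 − 150 = 45 ms, and 195 < 210.

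These examples show that such cases are possible. They say nothing about how often they would occur.

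**5. Two details that a numeric summary would need settled**

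- *Baseline for Cohort A6.* SAP 3.5.4 says "Baseline will be defined as the last non-missing evaluation prior to the first dose date/time" and resets Baseline only for Cohort A7 Period 2. SAP 1.2.1 says that "Baseline evaluations will be conducted prior to dosing in Cohort A6", and for the same cohort Appendix 1b, footnote a, says "Collection of ECG will be performed predose on Day 1". The measurement exists, but the SAP does not say that it is the Baseline. Taken literally, Baseline would be the value before the original fasted dose. With a minimum washout of 7 days, that value is at least 7 days old at A6 dosing.
- *Several ECGs in one day.* The appendices schedule post-dose ECGs at 2, 4 and 12 hours on Day 1 (Part A) and on Days 1, 3, 5 and 8 (Part B). SAP 5.5 says the table is by visit and does not mention time point. If one value per day were taken under SAP 3.5.6, the latest would be kept, so 1 of the 3 scheduled post-dose ECGs would be used. Section 5.5 does not say whether that rule applies.

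**The case against.** The best defence is that 10.4.4 speaks of ECG findings rather than ECG data and names no interval. Protocol 8.3.3 describes the 12-lead assessment as interpretation of tracings. Protocol 10.4 also says "Categorical endpoints will be described using the number and percent of subjects who meet the endpoint criterion", so a shift table with counts and percentages is descriptive and does compare each visit with Baseline. Appendix 4 is an adapted general grading table that includes items this trial does not measure, so its PR and QTc rows do not prove that an interval summary was intended. Finally, replicate ECG extraction belongs to Holter, while the 12-lead tracings after Screening are single.

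Part of this stands. That PR and QTc are the values meant is an inference from the change-from-Baseline wording and from Appendix 4. It does not remove the discrepancy. The protocol promises observed and change-from-Baseline values for both data types in one sentence, and the SAP's own definition of change is numeric. Holter data cannot fill the gap while they are only stored. If a categorical summary was the intention, the SAP should say so.

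The safeguards are real and limit the consequence. A physician reviews every ECG, assessment results are listed by subject, and confirmed, clinically significant abnormalities become AEs and are tabulated. The A6 Baseline and same-day questions are secondary, and the first also affects laboratory and vital-sign data.

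**Conclusion.** The concern holds. SAP 5.5 does not deliver the ECG summary that protocol 10.4.4 describes, and sections 1 to 8 of the SAP neither supply it elsewhere nor explain its absence. The text of SAP section 9 (Appendices) was not available, so the statement that no reason is given is limited to sections 1 to 8.

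The effect is confined to descriptive safety reporting. ECG is not part of the primary endpoint, post-Screening tracings are single, no inference is planned, and dose decisions rest on Data Review Committee review. Within that limit, interval changes would be absent from every summary table or shown without size, including a QTc rise that meets the protocol's own Grade 3 change limit. This should be corrected before the SAP is final; it does not threaten the trial's validity.

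**What to change.** Add to SAP 5.5 descriptive statistics for the ECG intervals, at least PR and QTc, as observed values and change from Baseline, by nominal time point, treatment and cohort. State the QT correction; Appendix 4 uses Bazett. Use the pre-dose Baseline of the relevant period for Cohort A7 Period 2 and for subjects returning in Cohort A6. Keep the shift table, and state that it is by time point or which same-day ECG it uses.

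Optionally, and beyond what 10.4.4 promises, count the subjects who meet the Appendix 4 PR and QTc limits, including the QTc rise of 0.06 s or more.

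If the intervals will not be summarised, record this in the SAP as a departure from 10.4.4, with the reason.

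The cost is SAP wording and a few tables. The eCRF was not available; if it does not capture the intervals, machine-read values would have to be transferred as well. No additional ECGs are needed, provided those values can be retrieved.
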